#### 10.7.2. Secondary Analysis

The virologic analysis will include comparison of the SCA levels pre-treatment (screening and entry) compared to post-treatment in Steps 5 and 6. We assume that the probability would be 0.10 (10%) for a baseline (pre-entry, entry) detectable SCA  $\geq 1$  copy and the probability would be at least 0.29 (29%) for a post-treatment measure for analyses. The assumption that 10% of participants with a quantifiable SCA at screening will have SCA below the limit of detection at a pre-treatment

measure is an estimate based on data from A5244 in which 6 of 50 (12%) enrolled participants had undetectable SCA at pre-entry and 5 of 51 (10%) at entry after having a screening SCA  $\geq 1$  copy [65].

For additional secondary endpoints, most endpoints are defined as change in a quantitative measure from baseline to post-infusion (e.g., change from baseline to week 13 in HIV-1 RNA by SCA). Assuming two-sided 0.05 significance, 5000 empirical simulations from a normal distribution with mean change equal to 1 standard deviation with n=12 evaluable participants achieved 85% power to detect a statistically significant change from baseline to post-infusion using an exact Wilcoxon signed-rank test (paired data). Thus, with n=12 there is reasonable power to detect a mean change of 1 standard deviation (SD) or larger. Observed virologic measurements may not be normally distributed or may be partially censored due to assay limits of quantification, and thus, an exact Wilcoxon signed-rank test will be used. Potential immune correlates of antiviral impact will be assessed via exact, non-parametric Spearman rank correlation based methods.

Descriptive statistics and graphical data displays will be used to summarize in vivo measurements of HIV-specific T-cells over the pre- to post-infusion period to assess the pattern and magnitudes of T-cell expansion and persistence for each virus. Measurements of immunity will be evaluated by descriptive statistics at each time point and analyzed by exact, nonparametric methods for paired data to compare changes from pre- to post-infusion. HIV-1 specific immune responses using standard immunoassays and measures of HIV-1 persistence will be analyzed similarly.

## **11. ETHICS/PROTECTION OF HUMAN SUBJECTS**

### **11.1. Ethical Standard**

The principal investigator will ensure that this study is conducted in full conformity with the principles set forth in The Belmont Report: Ethical Principles and Guidelines for the Protection of Human Subjects of Research, as drafted by the US National Commission for the Protection of Human Subjects of Biomedical and Behavioral Research (April 18, 1979) and codified in 45 CFR Part 46 and/or the ICH E6.

### **11.2. Institutional Review Board**

The protocol, informed consent form(s), recruitment materials, and all participant materials will be submitted to the IRB for review and approval. Approval of both the protocol and the consent form must be obtained before any participant is enrolled. Any amendment to the protocol will require review and approval by the IRB before the changes are implemented in the study.

### **11.3. Informed Consent Process**

Informed consent is a process that is initiated prior to the individual agreeing to participate in the study and continues throughout study participation. Extensive discussion of risks and possible benefits of study participation will be provided to participants and their families, if applicable. A consent form describing in detail the study procedures and risks will be given to the participant. Consent forms will be IRB-approved, and the participant is required to read and review the document or have the document read to him or her. The principal investigator or designee will explain the research study to the participant and answer any questions that may arise. The participant will sign the informed consent document prior to any study-related assessments or procedures. Participants will be given the opportunity to discuss the study with their surrogates and/or family/friends and think about it prior to agreeing to participate. They may withdraw consent at any time throughout the course of the study. A copy of the signed informed consent document will be given to participants for their records. The rights and welfare of the participants will be protected by emphasizing to them that the quality of their clinical care will not be adversely affected if they decline to participate in this study.

The consent process will be documented in the clinical and research record.

#### **11.4. Amendments**

Upon receiving final IRB/EC and any other applicable regulatory approval(s) for any amendment after Version 1.0, UNC should implement the amendment immediately. UNC is required to submit amendments to NHLBI. A copy of the final amendment approvals and documents issued by the NHLBI should be retained in the site's regulatory files.

#### **11.5. Participant Confidentiality**

All laboratory specimens, evaluation forms, reports, and other records that leave the site will be identified by coded number only to maintain participant confidentiality. All records will be kept locked. All computer entry and networking programs will be done with coded numbers only. Clinical information will not be released without written permission of the participant, except as necessary for monitoring by IRB(s), the FDA, the NHLBI, or the industry supporters or designee.

#### **11.6. Study Discontinuation**

The study may be discontinued at any time by the UNC-CH IRB, the NHLBI, the industry supporters, the FDA, or other government agencies as part of their duties to ensure that research participants are protected.

### **12. DATA COLLECTION, MONITORING, AND ADVERSE EVENT REPORTING**

## **12.1. Records to be kept**

Source documents will be provided for each participant. Participants will be identified by name in the source documents but will not be identified by name in the database or on any report associated with the study. Participants will be identified by the participant identification number (PID) and study identification number (SID) provided by the study database upon screening.

## **12.2. Role of the Data Manager**

It is the responsibility of the study site to assure the quality of data for this study. This role extends from protocol development to generation of the final study databases.

## **12.3. Clinical Site Monitoring and Record Availability**

### **12.3.1. Clinical Site Monitors**

Site monitors will visit the site to review the individual participant records, including consent forms, source documents, supporting data, laboratory specimen records, and medical records (physicians' progress notes, nurses' notes, individuals' hospital charts), to ensure protection of study participants, compliance with the protocol, and accuracy and completeness of records. The monitors also will inspect sites' regulatory files to ensure that regulatory requirements are being followed and sites' pharmacies to review product storage and management.

### **12.3.2. Site Investigators**

The site principal investigator will make study documents (e.g., consent forms, drug distribution forms, and source documents) and pertinent hospital or clinic records readily available for inspection by the local IRB, the site monitors, the FDA, the NHLBI, and the industry supporters or designee for confirmation of the study data.

### **12.3.3. Adverse Events Reporting to NHLBI**

All human participant research supported by NHLBI must include procedures for identifying, monitoring, and reporting all AEs, including both serious (SAE) and non-serious events, and UPs. All NHLBI human participant research will follow a uniform policy, which is based on the FDA/Office for Human Research Protections (OHRP) regulations and guidance including definitions and timelines.

The study site will reference the IRB-approved Study Progress and Safety Monitoring Plan (SPSMP) and report all SAE, AE, and UP Events per reporting timelines outlined in this document.

## 12.4. Reporting Requirements for this Study

The SAE Reporting Category, as defined in Version 2.0 of the DAIDS EAE Manual, will be used in this study. This SAE Reporting Category is redefined in the DSMP.

The study products, for which expedited reporting is required, are: HIV Expanded T-Cells (HXTC) and VOR.

## 12.5. Expedited AE Reporting Period

The expedited AE reporting period for this protocol is the entire study duration for an individual participant, once treatment is initiated (from study enrollment until study completion or discontinuation of the participant from study participation for any reason).

After the protocol-defined AE reporting period, unless otherwise noted, only suspected, unexpected serious adverse reactions (SUSARs), as defined in Version 2.0 of the EAE Manual, will be reported to NHLBI, FDA, or UNC IRB per their reporting requirements if the study staff become aware of the events on a passive basis (from publicly available information).

## 13. PUBLICATION/DATA SHARING POLICY

Publication of the results of this trial will be governed by NHLBI (NIH) policies. Any presentation, abstract, or manuscript will be made available for review by the industry supporters prior to submission.

## Appendix A: Schedule of Events (SOE)

	Step 1 Pre-Treatment			Step 2 p-2	Step 3 HXTc Production	
	Screen	Enrollment	Leukapheresis (#1)		Cell Collection for HXTc	Pre-Treatment Screen
Evaluations				Step 2 Eliminated		
Visit Window		≤30 days	≤45 days at or after enrollment		4-6 weeks after leukapheresis	4-10 weeks after Visit 5 ≤21 days before visit 6
Study Week						
Study Visit	1	2	2.1	3	4	5
Clinical Procedures						6
Consent, Eligibility, Demographics & Medical History	X			Step 2 Eliminated		
Assignment of PID	X					
Assignment of SID		X			X 	
Complete Physical Examination (vital signs & weight)	X					
Height ^	X					
Assess venous access	X					
Advancement Criteria			X			
Pre-Dose Clinical Assessment						X
Targeted Clinical Assessment 					X	X
Review medical history (including new medical conditions)		X			X	X
Assess Adverse Event	X		X		X	X
Review ART & ART Adherence	X	X	X		X	X
Review Concomitant Medication	X	X	X		X	X
Phone Assessment						
Vorinostat Administration (400 mg) (home)						
CTL Infusion						
CTL Pre-medication						
Post infusion assessment						
Leukapheresis (& meal)			X			
Clinical Laboratory Procedures				Step 2 Eliminated		
Chemistries	X 					X 
Coagulations (PT/INR/PTT)	X					
CBC with differential	X		X ∞			X
Pregnancy Test or FSH Test	X					X
CD4+ T Cell Differential Panel	X					X
HIV-1 RNA PCR	X					X
HBsAg & HCV Ab	X					X
Donor ID Panel 					X	
RPR	X					X
Urine Pregnancy – POCT 						
Urinalysis	X					
Research Laboratory Procedures				Step 2 Eliminated		
Single Copy Assay			X			X
PBMC for HDAC Responsive Gene Measurement		X 			X	
Single PK sample (VOR)					X	
Cells for CTL production					X	
HLA typing					X	
Immune Response, Viral Inhibition & Epitope Mapping		X 	X L		X	X 
Resting Cell Assay and CTL Latency						

Step 4: Second Series of VOR 400 mg x 10 doses at 72 hours and 2 HXTC infusions														
Evaluations		VOR Dose #1 and HXTC infusion #1	Safety check and research labs	VOR Dose #2	VOR Dose #3	VOR Dose #4	VOR Dose #5	VOR Dose #6 and HXTC Infusion #2	Safety check and research labs	VOR Dose #7	VOR Dose #8	VOR Dose #9	VOR Dose #10	Clinical Assessment – Pre-Step 5
Visit Windows - reference table in section 7.3.3														
Study Week		0			1		2			3		4	6	
Study Visit		7	8		9		10	11			12	13		
Clinical Procedures														
Consent, Eligibility, Demographics & Medical History														
Assignment of PID														
Assignment of SID														
Complete Physical Examination (vital signs & weight)														
Height														
Assess venous access														
Advancement Criteria														
Pre-Dose Clinical Assessment														
Targeted Clinical Assessment 														
Review medical history (including new medical conditions)														
Assess Adverse Event														
Review ART & ART Adherence														
Review Concomitant Medication														
Phone Assessment														
Vorinostat Administration (400 mg) (home)														
CTL Infusion														
CTL Pre-medication														
Post infusion assessment														
Leukapheresis (& meal)														
Clinical Laboratory Procedures														
Chemistries														
Coagulations (PT/INR/PTT)														
CBC with differential														
Pregnancy Test or FSH Test														
CD4+ T Cell Differential Panel														
HIV-1 RNA PCR														
HBsAg & HCV Ab														
Donor ID Panel 														
RPR														
Urine Pregnancy – POCT 														
Urinalysis														
Research Laboratory Procedures 														
Single Copy Assay														
PBMC for HDAC Responsive Gene Measurement														
Single PK sample (VOR)														
Cells for CTL production														
HLA typing														
Immune Response & Epitope Mapping														
Resting Cell Assay and CTL latency														

Step 5: Second Series of VOR 400 mg x 10 doses at 72 hours and 3 HXTC infusions													
Evaluations	VOR Dose #11 and HXTC infusion #1	Safety check research labs	VOR Dose #12	VOR Dose #13	VOR Dose #14	VOR Dose #15	VOR Dose #16 and HXTC Infusion #2	Safety check and research labs	VOR Dose #17	VOR Dose #18	VOR Dose #19	VOR Dose #20	
	Visit Window - reference table in section 7.3.4.												
	Study Week	8		9			10		11		12		
Study Visit	14	15					16	17			18	19	20
Clinical Procedures													
Consent, Eligibility, Demographics & Medical History													
Assignment of PID													
Assignment of SID													
Complete Physical Examination (vital signs & weight)													
Height													
Assess venous access													
Advancement Criteria													
Pre-Dose Clinical Assessment													
Targeted Clinical Assessment 	X	X					X	X		X	X	X	
Review medical history (including new medical conditions)	X	X					X	X		X	X	X	
Assess Adverse Event	X	X					X	X		X	X	X	
Review ART & ART Adherence	X	X					X	X		X	X	X	
Review Concomitant Medication	X	X					X	X		X	X	X	
Phone Assessment	(T)		(T)	(T)	(T)	(T)	(T)		(T)	(T)	(T)	(T)	
Vorinostat Administration (400 mg) (home)	X		X	X	X	X	X		X	X	X	X	
CTL Infusion	X						X					X	
CTL Pre-medication	X						X					X	
Post infusion assessment	X	X					X					X	
Leukapheresis (& meal)													
Clinical Laboratory Procedures													
Chemistries		X 					X 				X 		
Coagulations (PT/INR/PTT)													
CBC with differential		X					X 			X			
Pregnancy Test or FSH Test													
CD4+ T Cell Differential Panel													
HIV-1 RNA PCR													
HBsAg & HCV Ab													
Donor ID Panel 													
RPR													
Urine Pregnancy – POCT 	X 						X 				X 		
Urinalysis													
Research Laboratory Procedures 													
Single Copy Assay		X											
PBMC - HDAC Responsive Gene Measurement	X	X					X 	X		X	X	X	
Single PK sample (VOR)							X						
Cells for CTL production													
HLA typing													
Immune Response, Viral Inhibition & Epitope Mapping													
Resting Cell Assay and CTL latency													

Step 6; Immune Monitoring						
Evaluations	IM Visit #1	IM Visit #2 Eliminated	IM Visit #3 & Leukapheresis #2	IM Visit #4	IM Visit #5 Eliminated	IM Visit #6 Eliminated
Time to Visit	~ 7 days after Visit 19		~ 4 weeks after Visit 19	~ 9 weeks after Visit 19		
Visit Windows	3 days (+/-)		1 week (+/-)	1 weeks (+/-)		
Study Week	13		16	21		
Study Visit	21	22	23	24	25	26
Clinical Procedures						
Consent, Eligibility, Demographics & Medical History						
Assignment of PID						
Assignment of SID						
Complete Physical Examination (vital signs & weight)			X			
Height						
Assess venous access						
Advancement Criteria						
Pre-Dose Clinical Assessment						
Targeted Clinical Assessment 	X			X		
Review medical history (including new medical conditions)	X		X	X		
Assess Adverse Event	X		X	X		
Review ART & ART Adherence	X		X	X		
Review Concomitant Medication	X		X	X		
Phone Assessment						
Vorinostat Administration (400 mg) (clinic)						
CTL Infusion						
CTL Pre-medication						
Post infusion assessment						
Leukapheresis (& meal)			X			
Clinical Laboratory Procedures						
Chemistries	X 		X 			
Coagulations (PT/INR/PTT)						
CBC with differential	X		X ∞	X		
Pregnancy Test or FSH Test						
CD4+ T Cell Differential Panel	X		X	X		
HIV-1 RNA PCR	X		X	X		
HBsAg & HCV Ab						
Donor ID Panel 						
RPR						
Urine Pregnancy – POCT 						
Urinalysis			X			
Research Laboratory Procedures 						
Single Copy Assay	X		X			
PBMC for HDAC Responsive Gene Measurement						
Single PK sample (VOR)						
Cells for CTL production						
HLA typing						
Immune Response, Viral Inhibition & Epitope Mapping						
Resting Cell Assay and CTL Latency			X L	X		

## Legend

 CNH product ID will be assigned at this time.

^ Height will be obtained at screening in the CTRC – without shoes.

 Targeted clinical assessments are driven by signs and/or symptoms experienced since the last visit or unresolved signs or symptoms experienced previously and included weight and vital signs (temperature, blood pressure, pulse and respirations).

◊ Clinical labs for screening only include sodium (Na), potassium (K), chloride (Cl), bicarbonate (CO2), glucose, blood urea nitrogen (BUN), creatinine (Cr), calcium (Ca), magnesium (Mg), alanine aminotransferase (ALT), aspartate aminotransferase (AST), alkaline phosphatase (Alk Phos), total bilirubin (total bili). A direct bilirubin will be obtained if participant is on atazanavir. Lipase, albumin, total protein, triglyceride and cholesterol are obtained at screening and Visit 23 only.

 Clinical safety laboratory tests: Na, K, Cl, CO2, Cr, glucose, LT, AST, alk phos, total bili, Ca and Mg.

 Reference Study Specific Lab Manual for collection and processing requirements for research samples.

∞ CBC is required for Apheresis procedures. Labs for UNC can be obtained up to 24 hours prior to visit or STAT on the day of the procedure. The CBC for the American Red Cross or other local blood collection agency will be drawn per facility requirement up to 30 days prior to the collection.

 POCT pregnancy testing will be done on all women prior to initiation of VOR and at all HXTC infusions.

 Draw 25.5 mL (3 – 8.5 mL ACD tubes) at these selected time points.

↳ Samples come from the leukapheresis product and are sent to [name] Lab at UNC ambient for processing.

(T) Participants will be contacted via agreed upon communication mechanism to assess for adverse events.

 Labs may be obtained up to 48 hours prior to visit.

 Draw labs STAT, if done on day of visit. Results must be obtained and reviewed prior to procedure or infusion.

 If enrollment occurs on the day of the baseline leukapheresis, draw these samples on Visits 5 and 6, as indicated on the SOE.

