In this proposed study, participants will receive 10 doses of 400 mg VOR over a 30 day period, then no VOR for 4 weeks. They will then receive a second cycle of 10 doses of 400mg VOR over another 30 day period, for a total of 20 doses. Each participant will receive a total of 5 HXTC infusions; 2 infusions will be administered in the first 4 week cycle and 3 administered in the second 4 week cycle. In our previous study with VOR, most participants exhibited a 15%–35% transient decline in platelet count after 4 weeks of 3 daily doses each week. However, only one participant's platelet count reached grade 1 toxicity level. No other clinical events or drug-related AEs were observed. Given we now propose to administer fewer doses, over a shorter time (20 doses over 3 months), significant toxicity seems unlikely.

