Include all current medications and any PRN medications used within the past 30 days.

- All medication taken within 30 days of study screening.
- After study entry, record only new and discontinued over-the-counter, herbal, dietary and vitamin supplements, and prescription medications.
- Document all doses of VOR and HXTC therapy and permanent discontinuation.

8.1.1.14. **Signs, Symptoms, and Diagnosis of Illnesses and Diseases**

At screening, all signs and symptoms, regardless of grade, that occurred within the 30 days before entry must be recorded. After study entry, record any new diagnosis or illnesses that develop.

After study entry, grade  $\geq 3$  signs and symptoms must be recorded. Record only signs and symptoms that are related to VOR or HXTC therapy and all signs and symptoms that lead to a change in treatment, regardless of grade.

8.1.1.15. **Blood collection**

Please reference SOE in Appendix A

8.1.1.16. **Urine Collection**

Please reference SOE in Appendix A

8.1.1.17. **Assessment of adverse events**

Please reference protocol section 9.1

8.1.1.18. **Leukapheresis**

Participants will undergo two Leukapheresis procedures. The baseline leukapheresis will be completed at or after Visit 2. Participants will advance to Step 3 based on an IUPM measurement  $\geq 0.3$ . The 2nd leukapheresis will take place at the End of Study Intervention visit in Step 6, Visit 23.

All protocol required leukapheresis products will be transported on the day of collection to the [name] Laboratory on the UNC campus.

All leukapheresis procedures will occur at the UNC Apheresis Lab located in the UNC Blood Bank or at a local contracted blood collection center.

Note: Refer to the UNC Apheresis SOP and Study Specific Lab Manual for procedures specific to this study.

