### **10.2. Outcome Measures**

#### **10.2.1. Primary Endpoints**

##### **10.2.1.1. Safety**

Occurrence of at least one  $\geq$  Grade 3 adverse event including signs/symptoms, lab toxicities, and/or clinical events that is possibly or definitely related to VOR or HXTc any time from the first day of study treatment through Step 6, Visit 23.

Safety data will include local and systemic signs and symptoms, laboratory measures of safety/toxicity, and all adverse and serious adverse events. Safety data will be routinely collected throughout the duration of the study.

NOTE: The occurrence of a Grade 3 infusion reaction that is sustained for less than 48 hours will not be included as a primary safety endpoint.

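### The only blood count scheduled at Visit 23, where the primary safety window closes, may be up to 30 days old when leukapheresis is done off-site

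*Combined protocol and SAP*

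**What the plan says.** Section 10.2.1.1 defines the primary safety endpoint as at least one related Grade 3 or higher "adverse event including signs/symptoms, lab toxicities, and/or clinical events", occurring "any time from the first day of study treatment through Step 6, Visit 23".

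In Appendix A, the Step 6 table heads the Visit 23 column "IM Visit #3 & Leukapheresis #2". The CBC row has a plain mark at Visit 21, a mark with the apheresis footnote at Visit 23, and a plain mark at Visit 24. There is no second CBC mark at Visit 23.

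The legend says that the footnoted count is needed for apheresis. At UNC it may be taken up to 24 hours before the visit or on the day. For other centers the wording is "The CBC for the American Red Cross or other local blood collection agency will be drawn per facility requirement up to 30 days", counted back from the apheresis. Section 7.3.1.2 gives the same split between UNC and the Red Cross for Visit 2, as part of the leukapheresis procedure. Off-site collection is open to everyone under Section 8.1.1.18: "All leukapheresis procedures will occur at the UNC Apheresis Lab located in the UNC Blood Bank or at a local contracted blood collection center".

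The timing of Visit 23 after the last infusion (Visit 19) is stated in three ways: about 4 weeks, plus or minus 1 week (Appendix A); no sooner than 4 weeks (Section 10.1, for the second leukapheresis); and about 5 weeks (Section 4.6).

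**The concern.** A rule written to clear a person for apheresis also governs the only hematology value scheduled at the visit that closes the primary safety window. A site that follows the schedule exactly can close the window without a current count, and whether it does so depends on where the apheresis takes place, which is not a clinical reason.

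Hematology matters here because Section 2.2.5 names cytopenias among the three main categories of VOR adverse experience and reports, from an earlier VOR study, a "transient decline in platelet count after 4 weeks" of dosing.

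With 12 participants a single event moves the result. Section 10.4 gives one-sided 95% upper limits of 22% with no events and 34% with one.

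**Working it through.** All inputs come from Appendix A and Sections 4.6, 5.4, 7.3.4, 10.1 and 10.4. Days are counted from Visit 19 (HXTC #5) unless stated otherwise.

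**1. Reproduce the plan's calendar.** Visit 14 is Week 8, which is day 56 from Visit 7. Dose 20 is 27 days after dose 11, so day 83. Visit 19 follows 1 to 3 days later, on days 84 to 86.
- Visit 21: add 7 days, giving Week 13.0 to 13.3 (plan: 13).
- Visit 23: add 28 days, giving Week 16.0 to 16.3 (plan: 16).
- Visit 24: add 63 days, giving Week 21.0 to 21.3 (plan: 21).
- Visit 23 at the 5 weeks of Section 4.6: add 35 days, giving Week 17.0 to 17.3. This does not match the Week 16 that Section 4.6 also states.

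**2. Visit windows in days after Visit 19.**
- Visit 21: 7 ± 3 = day 4 to 10.
- Visit 23: 28 ± 7 = day 21 to 35.
- Visit 24: 63 ± 7 = day 56 to 70.

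**3. Earliest permitted off-site count = Visit 23 day − 30.**
- Appendix A timing: 21 − 30 = day -9, to 35 − 30 = day +5. At the nominal day 28 it is day -2. The count can pre-date the infusion on Visit 23 days 21 to 29, which is 9 of the 15 allowed days.
- Section 10.1, earliest case: 28 − 30 = day -2.
- Section 4.6: 35 − 30 = day +5, so it does not pre-date the infusion.
- At UNC, for comparison: 21 − 1 = day 20, to 35 (drawn on the day).

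**4. Can the Visit 21 count serve as the Visit 23 count?** It can if the two visits are at most 30 days apart. The smallest gap is 21 − 10 = 11 days, the nominal gap is 28 − 7 = 21, and the largest is 35 − 4 = 31. Of 7 × 15 = 105 day combinations, only day 4 with day 35 exceeds 30. The interval before Visit 23 without a count is therefore 11 to 30 days.

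This does not depend on which timing applies. With Visit 23 on day 28 to 35 the interval is 28 − 10 = 18 up to 30 days. At day 35 it is 35 − 10 = 25 up to 30 days.

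**5. Next count after Visit 21 if it is reused.** Visit 24 is 56 − 10 = 46 to 70 − 4 = 66 days later, after the primary window. It also falls after the six weeks (day 42) that Section 6.1.7 sets for monitoring infusion-related events.

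**6. Participants who stop early.** Section 5.5.1 moves them to Visit 23, although Section 9.3 asks them to continue scheduled evaluations, so a Visit 21 count is not assured. Section 5.4 puts their Visit 23 at 4 to 8 weeks after the last documented visit or treatment, whichever is later. If they have off-site leukapheresis, the earliest count is 28 − 30 = day -2 to 56 − 30 = day +26 from that anchor. Where the anchor is the last treatment and Visit 23 is on day 28, all 28 post-treatment days could lack a count.

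**7. Weight of one event.** With none in 12, the one-sided 95% limit is 1 − 0.05^(1/12) = 22.1%. With one in 12, the exact limit is 33.9%. Both agree with Section 10.4.

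**The case against.** The strongest case against rests on five points.

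- **There are other counts.** A reader might infer that hematologic toxicity after the last infusion goes wholly undetected. The documents do not support that. Visit 21 has its own CBC without the early-draw allowance, inside the window, and Visit 24 has another.
- **A late finding is still reported.** Section 10.7.1 describes all treatment-related events through the end of study, Section 9.2.3 collects events to 30 days after Visit 24, and the two-participant suspension rule in Section 10.5 applies throughout. An event first seen at Visit 24 might fall outside the formal primary count, but not outside reporting or monitoring.
- **The risk is modest.** Section 2.2.5 says that hematologic events generally reversed quickly once VOR was interrupted, and that only one earlier participant's platelet count reached Grade 1. Visit 21 is 4 + 1 = 5 to 10 + 3 = 13 days after the last VOR dose, so VOR-related cytopenia should be resolving by then.
- **The stopping rule is not affected in completers.** A reader might infer that an old count defeats the hematologic discontinuation rule in Section 5.5.1. That rule governs further VOR and HXTC, and a completer has none left after Visit 19.
- **The note may be meant for clearance only.** Section 8.1.2.5 calls for a CBC and chemistries at required visits, chemistries are marked at Visit 23, and 30 days is a ceiling subject to facility rules.

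The first four points stand and limit the size of the problem. The fifth stands only in part. Section 8.1.2.5 sets no separate timing, Section 7.3.5.2 refers Visit 23 procedures back to the schedule, and the schedule has no other CBC mark there. Reuse of the Visit 21 count is permitted; whether sites would do it is not known.

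**Conclusion.** The point holds in a limited form. For off-site leukapheresis, the plan allows the primary safety window to close with 11 to 30 days since the last count in a participant who completes treatment. A Grade 3 or higher cytopenia arising in that interval could be missed if transient, or first seen after the window closes if it persists. Among participants who stop early, go straight to Visit 23 and have off-site leukapheresis, more of the post-treatment period may be uncovered.

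That the count can pre-date the last infusion rests on the visit timing. It is possible under Appendix A and, at exactly 4 weeks, under Section 10.1, but not at 5 weeks. The late gap remains under all three.

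The size also rests on two assumptions: that sites use the full allowance or reuse the Visit 21 count, and that some collections are off-site. The documents do not give that number, so it could be anywhere from 0 to 12 of the 12 participants. The probability of a missed event is low. This is an inexpensive improvement, not a flaw that undermines the safety analysis.

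**What to change.** In the legend and the Visit 23 cell of Appendix A, restrict the 24-hour and 30-day rule to clearance for apheresis. Add a separate Visit 23 safety CBC with differential, drawn at the visit with the chemistries and before apheresis, whichever center collects. State in Section 10.2.1.1 that this value is the Visit 23 hematology result for the primary safety endpoint. Reconcile the timing of Visit 23 across Appendix A, Section 4.6 and Section 10.1.

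The cost is one legend line, one schedule mark, a sentence in Section 10.2.1.1, and one extra CBC tube per participant collected off-site, at a visit that already draws chemistries and up to 70 mL of blood. The treatment and the planned tests do not change.
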